### **Mite Stages Visible by RCM**

The presence of adult mites, juvenile mites, eggs and scybala observed over time will be assessed in an exploratory manner using descriptive summaries.

A summary will present the number and percentage of subjects with at least one lesion identified as having presence of each of the following respectively, by dose group and RCM time point: adult mites, juvenile mites, eggs, scybala. The table will additionally present the number and percentage of subjects recording presence of any one of

these options in at least one lesion, by dose group and RCM time point. The denominator for all percentages will be the number of subjects in the population for the respective dose group.

There will be no imputation of missing or inconsistent data for individual lesions prior to summary of the responses for mite stages present. Presence of a mite stage will be determined from all non-missing lesion assessments at the respective time point for the subject, including lesions assessed as no longer visible (assumed to have no mite stages present). The summary may therefore include subjects with missing lesion assessments where at least one assessment is non-missing. Subjects with completely missing RCM assessment data for all lesions at a time point will be included under a 'Missing' category for the respective summary.

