| Specialized analyses:                  | 
Pharmacodynamics
 
RCM will be used to evaluate the presence, number and morphology of S. scabiei mites by stage (adults, juvenile stages) and the presence of eggs and scybala within a minimum of 2 scabies lesions.
 
Z-stack photos of mites, eggs and scybala in each of the lesions will be obtained at the following time points:
 
 
• Baseline (up to 60 minutes prior to dosing);
 
• Hours 4, 8, 24, 48 and 72; and,
 
• Days 7, 14 and 28 after dosing.
 
 
Clinician reported outcomes, including assessment of scabies signs and symptoms, will be performed by the Investigator at the following time points:
 
 
• Baseline (within 60 minutes prior to dosing)
 
   |

|                                   |  |
|-----------------------------------|--|
|                                   | 
 
• Days 7, 14 and 28 after dosing.
 
 
Patient reported outcomes will be captured through the relevant questionnaires administered to the subject at the following time points:
 
 
• Baseline (within 60 minutes prior to dosing)
 
• Days 7, 14 and 28 after dosing.
 
 
Pharmacokinetics
 
Blood will be drawn for analysis of plasma moxidectin concentrations at the following time points:
 
 
• Baseline (within 15 minutes prior to dosing)
 
• Hours 2, 3, 4, 8, 24, 48 and 72 and Days 7, 14 and 28.
 
 
NOTE: pharmacokinetic sampling and pharmacodynamic assessment should be conducted within a 15 minute window of each other.
   |
| Sample size determination: | No formal sample size calculations were performed for this study. Dose cohorts of approximately n = 6 are considered to be practical and adequate to provide information for the full characterization of pharmacokinetics across the dose range.  |

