### 2.2 Study Endpoints

The primary endpoints of the study are as follows:

- Efficacy will be determined by death of the mites, defined as the degradation (loss of internal and/or external anatomic structures) of the adult mite observed by reflectance confocal microscopy (RCM). Mites will be assessed at Hours 4, 8, 24, 48 and 72 and Days 7, 14 and 28 in not less than two lesions nominated pre-treatment.
- Safety will be assessed by the incidence and severity of adverse events (AEs), physical examinations, and measurement of vital signs up to and including Week 12, and laboratory safety parameters up to and including Day 28.

The secondary endpoints are the key exposure metrics for moxidectin including area under the concentration time curve (AUC) and maximum plasma concentration ( $C_{max}$ ), which will be determined by non-compartmental analysis of moxidectin pharmacokinetic parameters or other methods as appropriate, assessed up to and including Day 28.

The exploratory endpoints are:

- At Hours 4, 8, 24, 48 and 72 and Days 7, 14 and 28, using assessment by RCM of burrows selected pre-treatment:
  - Changes in adult mite motility (peristalsis and/or movement) over at least 30 seconds of observation;
  - Presence, number, morphology and motility of juvenile scabies mites;
  - Presence of eggs and scybala in burrows.
- Presence and total number of mites and burrows assessed visually at Days 7, 14 and 28.
- Changes in assessment of clinician-reported scabies symptomology, including extent of symptoms on body regions assessed by the number of anatomically-defined regions affected, number of lesions and severity grading of excoriations and erythema.
- Changes in patient reported outcomes, measured by Numerical Rating Scale, 5-D Itch Scale and Dermatology Life Quality Index.
- Clinical cure rates at Days 7, 14 and 28. Clinical cure is defined as resolution of all scabies signs and symptoms present at Baseline, no new scabies signs and symptoms and no evidence of mites by dermoscopy.

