## **6.10 Efficacy Evaluation**

### **6.10.1 Primary Endpoint**

#### **6.10.1.1 Primary Variable**

The primary efficacy endpoint of the study will be determined by the death of adult scabies mites at each post-Baseline RCM assessment, with death defined as the degradation (homogenization of internal structures and/or external anatomic structures, and increased reflectance) of the adult mite observed by RCM.

A minimum of 2 and maximum of 4 live adult scabies mites, each within its own distinct lesion, will be identified at Baseline by RCM for each subject. Only those lesions confirmed by RCM to contain a live adult scabies mite at Baseline will be recorded on the eCRF. These identified lesions will then be further assessed by RCM at Hours 4, 8, 24, 48 and 72 and Days 7, 14 and 28 for changes in mite morphology, movement and peristalsis.

For the purposes of analysis of the primary variable, only the 2, 3 or 4 individual live adult mites identified at Baseline by RCM will be evaluated at post-Baseline time points. It is not expected that juvenile mites will mature into adults within a selected lesion being evaluated for the primary endpoint. If there is evidence to suggest that this has occurred, the data will be reviewed on a case by case basis to determine how this should be handled in the analysis.

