### **Presence, Number, Morphology and Motility of Juvenile Mites**

The presence and characteristics of juvenile mites observed over time will be assessed in an exploratory manner using descriptive summaries.

The total number of juvenile mites across all subjects, the total number and percentage of lesions across all subjects that were assessed and the total number and percentage of lesions across all subjects where any juvenile mites were observed will be presented by dose group and RCM time point. The table will also present the total number and percentage of lesions across all subjects with each of the responses to whether any juvenile mite has intact morphology (intact/not intact/unsure), as well as the total number and percentage of lesions across all subjects where any juvenile mite does/does not exhibit movement or peristalsis respectively, by dose group and RCM time point. The denominator for all percentages will be the total number of lesions identified at Baseline across all subjects.

There will be no imputation of missing or inconsistent data prior to the summary of the juvenile mite responses. Missing responses (due to the subject missing the complete RCM assessment or missing the individual lesion assessment) will be included under a 'Missing' category for each respective summary. Where juvenile mites are recorded as no longer present or where a lesion is recorded as no longer visible, responses will be assumed as follows: 'not intact' for morphology, 'without movement' and 'without peristalsis' for motility.

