### **6.15 Changes from the Protocol Planned Analysis**

- The definition of the FAS has been amended to remove the statement regarding the requirement for 'observed data for the particular analysis undertaken'. Instead, the inclusion/exclusion of subjects with missing data in analyses and summaries of the relevant endpoints on the FAS is addressed via the methods for handling missing data, as described in the respective sections of this SAP.

In addition, some imputation of missing data has been incorporated with respect to analysis and summary of the primary endpoint, rather than exclusion of any subjects with missing observations. These changes were considered more appropriate to ensure closer adherence to the intent to treat principle as well as to ensure clarity regarding the subjects included in the population and in each respective analysis.

- The exploratory endpoint 'presence of eggs and scybala in burrows' has been addressed via the summary of 'mite stages visible by RCM'.

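### Eggs and scybala are read in each of 2 to 4 lesions but tabulated only as subjects with any positive lesion, which damps change; a lesion-level row would recover the information at almost no cost

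*SAP*

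**What the plan says.** SAP 2.2 lists as an exploratory endpoint "Presence of eggs and scybala in burrows", assessed by RCM at Hours 4, 8, 24, 48 and 72 and Days 7, 14 and 28. Reading is by lesion. SAP 6.10.1.1 has "A minimum of 2 and maximum of 4 live adult scabies mites, each within its own distinct lesion" identified at Baseline, and the protocol synopsis says "Z-stack photos of mites, eggs and scybala in each of the lesions will be obtained at the following time points", listing Baseline and the eight later times.

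The summary is by subject. SAP 6.10.3.1, *Mite Stages Visible by RCM*, presents the "number and percentage of subjects with at least one lesion identified as having presence of each of the following respectively", naming adult mites, juvenile mites, eggs and scybala, with a further row for any of them. On the denominator it says: "The denominator for all percentages will be the number of subjects in the population for the respective dose group". SAP 6.15 states that the eggs-and-scybala endpoint is addressed through this summary, and no other SAP table covers it.

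The other two stages in that table also have a finer summary within 6.10.3.1. Adult mites are tabulated per mite. For juvenile mites the plan gives the "total number and percentage of lesions across all subjects where any juvenile mites were observed", with Baseline lesions as denominator and a Missing category.

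**The concern.** Collapsing 2 to 4 readings into any or none discards most of what was recorded. A subject who goes from eggs in 4 of 4 lesions to eggs in 1 of 4 is tabulated as unchanged. The indicator also rises mechanically with the number of lesions followed. That number varies between subjects, and with about 6 subjects per dose group it need not balance across arms.

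At stake is how clearly the tables describe the effect on life-cycle stages, which is an exploratory objective of the study. The data that would show it are collected anyway, and the SAP already has a format for them.

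**Working it through.** The plan states no expected rate, effect or power for this endpoint, so there is no figure of its own to reproduce.

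**Inputs.** From the documents: m = 2, 3 or 4 lesions per subject (SAP 6.10.1.1) and about 6 subjects per dose group (SAP 3). Assumed, because the documents give neither: the per-lesion egg rate p and the within-subject correlation.

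**1. Bound that needs no egg rate beyond the starting point.** Let all 6m lesions be positive at Baseline. The table reads 6/6 as long as each subject keeps one positive lesion, so 6 lesions suffice. The largest hidden fall is 1 − 6/(6m) = 1 − 1/m.

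| Lesions each | Positive lesions | Hidden fall | Planned table |
|---|---|---|---|
| 2 | 12/12 to 6/12 | 50% | 6/6 to 6/6 |
| 3 | 18/18 to 6/18 | 67% | 6/6 to 6/6 |
| 4 | 24/24 to 6/24 | 75% | 6/6 to 6/6 |

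**2. Dependence on the number of lesions.** With independent lesions the any-lesion rate is 1 − (1 − p)^m. At an assumed p = 0.30:
- m = 2: 1 − 0.7² = 51%
- m = 4: 1 − 0.7⁴ = 76%

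The same infestation therefore reads 25 points apart.

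**3. Typical rather than extreme damping.** Let p halve from 1.0 to 0.5, with independent lesions. The expected subject-level figure goes from 100% to 75% (m = 2), 87.5% (m = 3) or 93.8% (m = 4). The chance that all 6 subjects still read positive is 0.75⁶ = 18%, 0.875⁶ = 45% or 0.9375⁶ = 68%.

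Over Baseline rates of 0.6 to 1.0, a 50% relative fall in lesions shows as about 25% to 39% (m = 2) or 6% to 22% (m = 4). With a beta-binomial model, correlation 0.1 to 0.5 and Baseline rates of 0.6 to 0.9, it shows as about 31% to 44% (m = 2) or 14% to 38% (m = 4). Correlation weakens the damping but does not remove it.

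**4. Ranking two arms.** This is the measure closest to a descriptive comparison. Trials of 6 vs 6 were simulated with 2 to 4 lesions per subject (uniform), beta-binomial presence and correlation 0, 0.2 or 0.4. Entries are the percentage of trials in which the arm with the higher true rate shows the higher figure. The range is over the correlations, and repeat runs differ by a point or two.

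| Per-lesion rates | Any-lesion table | Mean per-subject proportion |
|---|---|---|
| 90% vs 50% | about 60% to 80% | about 98% or more |
| 90% vs 40% | about 79% to 91% | over 99% |
| 80% vs 30% | about 90% to 93% | about 99% or more |
| 70% vs 30% | about 87% to 89% | about 97% or more |

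Most any-lesion misses are ties. Outright reversals are no more than about 4%.

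**The case against.** **The wording asks only for presence.** The SAP asks for number, morphology and motility of juvenile mites but only presence of eggs and scybala, and Protocol 15.1 makes the subject the usual unit of analysis. A subject-level row answers a fair question: is any egg still visible in this subject's followed lesions? This stands. The planned row is legitimate and should stay, and SAP 6.15 contains no error. It does not explain why juvenile presence, equally exploratory, is tabulated per lesion while egg presence is not.

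**The information is not lost for good.** SAP 6.10.1.4 lists all RCM data, and SAP 6.10.3 allows further post-hoc analyses. Both are true, and they limit the weight of the point. Counting lesions by hand over nine time points is a poor substitute for a table row, though. The post-hoc route is optional and follows review of summaries that may show nothing to pursue.

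**Stronger readings that the documents do not support.**
- A reader might infer that the any-lesion table cannot separate doses, or that it sits near 100% until almost every lesion is clear. The ranking results and the 51% at a 30% rate contradict both.
- A reader might compare power. With two-sided 5% tests and correlation 0 to 0.4, the three lower rows of the ranking table give 1% to 8% for the any-lesion indicator and 34% to 78% for the proportion. But SAP 6.10.3 plans descriptive summaries. At 6 vs 6, Fisher's test reaches 5% only at 6/6 vs 0 or 1, at 5/6 vs 0, and at the mirror images, so any binary outcome would fare badly.
- A reader might tie eggs to the case for a single dose. Protocol 5.2 and 5.4.1 say ivermectin is not ovicidal, but no section says moxidectin is. Protocol 5.4.2 expects it to eliminate hatching mites, which the juvenile and adult tables address.

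**Conclusion.** The point holds as a minor one. The only planned summary of eggs and scybala damps change and varies with the number of lesions followed. In the limiting case it hides a fall of 50% to 75% in egg-bearing lesions. That bound rests only on all lesions being positive at Baseline and each subject keeping one positive lesion. The expected damping and the ranking figures rest on assumed egg rates and correlations. In every scenario run the any-lesion figure did worse than the per-subject proportion, though it still ranked the arms correctly more often than not.

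The loss is confined to an exploratory, descriptive table. No primary or secondary endpoint depends on it, and the matters named in SAP 5.1 to guide the steering committee are adult-mite death, safety and pharmacokinetics.

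**What to change.** In SAP 6.10.3.1, *Mite Stages Visible by RCM*, add for eggs and for scybala, by dose group and RCM time point:

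- the number and percentage of Baseline lesions with the stage present, with a Missing category, in the format of the juvenile-mite table;
- descriptive statistics of the per-subject proportion of lesions with the stage present, which keeps the subject as the unit and avoids treating lesions from one subject as independent.

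Keep the any-lesion rows. SAP 6.15 needs no correction; a cross-reference to the added rows is optional.

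The cost is a few lines of SAP text and a few rows in an existing table shell. No new data, visits or subjects are needed.

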### **6.10.3.2 Clinician Reported Scabies Signs and Symptoms**

Subjects will be assessed for the clinical signs and symptoms of scabies infestation at Baseline, Day 7, 14 and 28. The following exploratory endpoints will be assessed using this data:

- Presence and number of total mites and burrows assessed visually at Days 7, 14 and 28.
- Changes in assessment of clinician-reported scabies symptomology, including extent of symptoms on body regions assessed by the number of anatomically-defined regions affected, number of lesions and severity grading of excoriations and erythema.

The clinician reported scabies signs and symptoms endpoints will be assessed in an exploratory manner using descriptive summaries.

Summaries will be presented for the number of subjects exhibiting each of the parasitological and clinical features, as well as those with new signs and symptoms, across all regions assessed for the subject by dose group and visit. These summaries will include the number and percentage of subjects with any:

- Mites;
- Burrows;
- Any parasitological features (mites or burrows);
- Lesions;
- Nodules;
- Excoriations (overall and by grade of excoriation);
- Erythema (overall and by grade of erythema);
- Any clinical features (lesions, nodules, excoriations or erythema);
- Any parasitological or clinical features (mites, burrows, lesions, nodules, excoriations or erythema);
- New mites relative to previous visit;
- New burrows relative to previous visit;
- New lesions relative to previous visit (including 'Yes' or 'Unsure');

- Region status at post-Baseline visits ('New region', 'Region clear from previous assessment').

The denominator for all percentages will be the number of subjects in the dose group with a non-missing assessment for at least one region at the respective visit and this will also be presented in the summaries. If a region is assessed as clear from previous assessment, it will be assumed to have no parasitological or clinical features present. If a region is new compared to the previous assessment, all mites, burrows or lesions detected at that region will be assumed to be new.

In addition to the above, the number of anatomical regions affected per subject will be summarized using descriptive statistics. This summary will exclude any regions recorded as clear from previous assessment.

A further summary table will present the number and percentage of subjects recording each of the following lesion number categories by anatomical region, dose group and visit:

- 0 lesions;
- 1-10 lesions;
- 11-20 lesions;
- 21-30 lesions;
- 31-40 lesions;
- 41-50 lesions;
- >50 lesions;
- Total subjects with any lesions.

The denominator for all percentages will be the number of subjects with a non-missing assessment for the respective region, visit and dose group and this will also be presented in the summary. If a region is assessed as clear from previous assessment, it will be assumed to have zero lesions present. Only regions with at least 1 subject presenting with at least 1 lesion at any visit will be presented. Regions where no lesions are present for any subject at any visit will not be presented.

Further summaries will also be presented for the following:

- Number of mites per subject across all anatomical regions, by dose group and visit.
- Number of burrows per subject across all anatomical regions, by dose group and visit.

Descriptive statistics for these summaries will include all subjects with a non-missing assessment for at least one region for the dose group and visit. If a region is assessed as clear from previous assessment, it will be assumed to have zero mites or burrows present respectively.

All scabies signs and symptoms data will be listed.

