### **6.2 General Derivations**

This section provides details of general derivations. Derivations specific to a parameter of interest are detailed within the specific SAP sections.

- **Definition of study day**

Throughout this SAP any references to 'Day XX' refer to the pre-specified visits defined in the protocol (where the study drug administration visit is Day 0).

Data listings by visit will additionally present the duration from the administration of study drug in days, referred to as 'Study Day XX'. Study Day will be calculated relative to the date of administration of study drug in whole days. Thus, assessments completed on the day of study drug administration ('Day 0' visit) will be assigned a Study Day value of 1.

- **Definition of Baseline**

Baseline is defined as the last non-missing value (including scheduled and unscheduled assessments) prior to the subject receiving study drug.

- **Incomplete dates**

For calculation purposes, incomplete dates will be completed using a worst case approach. For example, assuming the earliest or latest possible date given all available information to ensure a worst case applies for each respective case. Further details are provided in the relevant sections as required.

- **Non-numeric values**

In the case where a variable is recorded as " $> x$ ", " $\geq x$ ", " $< x$ " or " $\leq x$ ", then for analysis purposes a value of  $x$  will be taken. Where a range of values is quoted, the midpoint of the range will be taken.

- **Site pooling for statistical analyses**

No analysis by center or country will be performed due to the small sample size of the study. Subjects from all centers will be pooled for summaries and analyses.

- **Methods for handling withdrawals and missing data**

In general, data will not be imputed unless otherwise stated in relevant sections.

- **Definition of planned dose and actual dose received**

Planned dose of study drug is defined as the dose group to which the subject was randomized and will be determined by the randomization list. Actual dose received is defined as the actual dose of study drug received regardless of randomized dose group. This will be determined once the blind has been broken using details provided by MDGH and/or captured on the electronic Case Report Form (eCRF) regarding actual doses received by subjects.

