#### **6.10.3.4 Clinical Cure Rate**

Clinical cure rate is defined as resolution of all scabies signs and symptoms present at Baseline, no new scabies signs and symptoms and no evidence of mites by dermoscopy.

Clinical cure rate will be assessed at Days 7, 14 and 28. At each of these visits, a subject will be considered a responder, as determined by the clinician reported scabies signs and symptoms, if region status is 'Region clear from previous assessment', for each anatomical region assessed at that visit.

For each subject, imputation of missing assessments will be applied as follows. Where the scabies signs and symptoms assessment has been completed for a visit but this includes a missing assessment for a region previously assessed at an earlier time point, the region status will be imputed using the most recent previous assessment for the respective region (last observation carried forward). However, if the scabies signs and symptoms assessment has not been completed for a visit, or the assessments for all regions previously assessed are missing, no imputation will be applied and the subject will be excluded from the denominator for clinical cure rate at that visit.

Where rescue medication has been taken (identified on the concomitant medications page of the eCRF), any assessment indicating clinical cure response subsequent to the start date of rescue medication will be ignored and the subject will be considered a non-responder. Visit responses identified at any visit prior to or on the start date of rescue medication for the subject will be unaffected.

The number and percentage of responders, together with the Clopper-Pearson 95% CI for the percentage, will be presented for each dose group at each post-Baseline visit. The denominator for all percentages will be the number of subjects with a non-missing scabies signs and symptoms assessment for the respective dose group and visit and this will also be presented in the summary.

A flag will be added to the listing of scabies signs and symptoms data to indicate subjects identified as responders at each time point.

Following review of the above summaries, additional post hoc analyses may be considered, for example sensitivity analyses repeating the above clinical cure rate summary without imputation for missing assessments or the use of rescue medication. Any post-hoc analyses to be performed will be fully defined in a SAP Addendum prior to conducting the analyses.

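### In the exploratory burden summaries, a previously affected region or lesion left unexamined at a visit adds nothing, so a partial examination can read as improvement or clearance

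*SAP*

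**What the plan says.** Three sets of summaries in the SAP's exploratory section are involved.

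**Presence of features (6.10.3.2).** The percentages with any mites, burrows, lesions or other features use as denominator the "number of subjects in the dose group with a non-missing assessment for at least one region at the respective visit".

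**Per-subject totals (6.10.3.2).** The count summaries are described as "Number of mites per subject across all anatomical regions, by dose group and visit", with a parallel line for burrows. On who is included: "Descriptive statistics for these summaries will include all subjects with a non-missing assessment for at least one region for the dose group and visit". The only zero rule concerns a region that was examined: "If a region is assessed as clear from previous assessment, it will be assumed to have zero mites or burrows present respectively". The count of regions affected has no inclusion rule of its own, only "This summary will exclude any regions recorded as clear from previous assessment".

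**Mite stages by RCM (6.10.3.1).** "Presence of a mite stage will be determined from all non-missing lesion assessments at the respective time point". The denominator is all subjects in the dose group, and only a subject with no lesion assessed at all goes into the 'Missing' category.

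The default in 6.2 is: "In general, data will not be imputed unless otherwise stated in relevant sections". Section 6.10.3.2 states no imputation. For clinical cure, 6.10.3.4 does foresee a completed visit with one previously assessed region missing. In that case "the region status will be imputed using the most recent previous assessment for the respective region".

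**The concern.** The SAP recognises, in the cure section, that a visit can be completed with a region left out. The section that tabulates the same examination as counts and percentages does not deal with that case. Its inclusion rule admits the partly examined subject, and with nothing imputed the subject's total can only be the sum over the regions examined. A region last seen affected then contributes what a cleared region contributes.

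The error has a known direction in the case that matters. At a post-Baseline visit, leaving out a region or lesion last seen affected cannot raise the burden. If the region has truly cleared, the zero is right; if not, the figure is too low. With about 6 subjects per dose group, and a study whose stated approach is to see descriptively which dose looks best, one or two partial examinations can shift a dose comparison without any trace in the table.

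**Working it through.** There is no stated figure to reproduce. The check is a comparison of rules, followed by illustrations with assumed inputs.

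**Rules side by side, for a previously affected region or lesion not assessed at a completed visit**

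| Summary | Treatment of the gap |
|---|---|
| Any mites, burrows or other feature (6.10.3.2) | Subject stays in the denominator; the region cannot count as present (implied) |
| Mite and burrow totals (6.10.3.2) | Subject included; the region adds 0 (implied) |
| Regions affected (6.10.3.2) | Region uncounted (from silence) |
| Mite stages (6.10.3.1) | Judged on the assessed lesions only (stated) |
| Lesion-number categories (6.10.3.2) | Region-specific denominator, so the region drops out |
| Adult motility and juvenile tables (6.10.3.1) | 'Missing' category for the lesion (stated) |
| Clinical cure (6.10.3.4) | Last status of that region carried forward (stated) |

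A subject with four Baseline lesions, one assessed and clean and three not assessed, is therefore scored as having no mite stages.

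**Illustration 1: counts.** Assumed: 12 mites spread evenly over 4 regions (3 each), no true change, one region missed.
- Recorded total: 12 − 3 = 9. Apparent fall: 3/12 = 25%.
- Arm of 6, the others unchanged at 12: (5 × 12 + 9)/6 = 69/6 = 11.5. Apparent fall in the mean: 0.5/12 = 4.2%.
- With the subject's total set to missing: (5 × 12)/5 = 12, n = 5.
- Range: missing one of R equally affected regions gives a false fall of 1/R, that is 50% for R = 2, 25% for R = 4 and 16.7% for R = 6.

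**Illustration 2: presence.** Assumed: 6 subjects, every examined region clear, and c subjects each with one unassessed region last seen with mites. One subject is 1/6 = 16.7 percentage points.

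| c | Any mites, SAP rule | Any mites, region carried forward | Present / absent / missing, proposed rule | Cure, 6.10.3.4 |
|---|---|---|---|---|
| 1 | 0/6 | 1/6 (16.7%) | 0 / 5 / 1 | 5/6 (83.3%) |
| 2 | 0/6 | 2/6 (33.3%) | 0 / 4 / 2 | 4/6 (66.7%) |
| 3 | 0/6 | 3/6 (50.0%) | 0 / 3 / 3 | 3/6 (50.0%) |

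The any-mites result stays at 0/6 however many examinations are incomplete. In this scenario the row for any parasitological or clinical feature and the regions-affected count also show nothing for subjects whom the cure table scores as non-responders at the same visit.

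**The case against.** Much of the opposing case is sound and limits the point.

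- **The zero in 6.10.3.2 is not written anywhere.** It follows from the inclusion rule plus the no-imputation default. The table shells and the study reference manual are separate documents and might say more. This stands. It does not apply to the mite-stage table, where the rule is stated.
- **The cure rule carries forward the last status, whatever it was.** A region last recorded clear is carried forward as clear, and the two sections agree. The disagreement is confined to regions last seen affected.
- **A reader might infer that a subject who is not cured but has no mites shows the tables contradicting each other.** The documents do not support that. Cure requires all signs and symptoms to resolve, and the protocol expects symptoms to outlast the infestation. Cure also overrides responses after rescue, while the other exploratory summaries ignore rescue. The true mismatch is the one shown under Illustration 2.
- **A reader might infer that missing data always favour efficacy.** That is too strong. A region last seen clear changes nothing. A region missed at Baseline lowers the Baseline burden, and features found there later count as new, which works the other way.
- **A reader might take a very large effect as typical.** Three of four regions unexamined would give 9/12 = 75%, but nothing in the documents suggests that extent. They give no rate of missing regions and no account of subjects declining part of the examination.
- **The RCM rule is an open choice.** The SAP says that partly assessed subjects may be included, and the adult motility table reports how many subjects have an incomplete lesion assessment. That discloses the gap but does not correct the percentage.
- **The stakes are modest.** These are exploratory summaries. The primary endpoint carries mite status forward, and committee review is guided by mite mortality or time to death, plus safety. Listings and optional post-hoc analyses exist, but they leave the planned tables as they are.

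**Conclusion.** The point holds in limited form. In the presence percentages, mite and burrow totals and regions-affected count of SAP 6.10.3.2, a previously affected but unexamined region implicitly counts as none. In the mite-stage table of 6.10.3.1, a partly assessed subject with clean assessed lesions is explicitly scored as having no mite stages. After Baseline, for regions or lesions last seen affected, this can only lower the apparent burden or leave it unchanged. It reads as full clearance only when everything examined is clear; otherwise it reads as a reduction.

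The sizes are illustrative: a 25% false fall for one subject, 4.2% in the mean of an arm of 6, and 16.7 points on any mites for each subject wrongly read as clear. They rest on assumed mite numbers, an even spread and no true change. The actual effect depends on how often regions are missed, which the documents do not say. The primary endpoint is unaffected. The correction is worth making because it is cheap and the SAP already uses better rules in neighbouring tables.

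**What to change.** Amend the SAP before the Day 28 blind break:

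1. **Presence tables (6.10.3.2 and mite stages in 6.10.3.1).** Score a feature as present if it is seen in any assessed region or lesion. Score it as absent only if every previously affected region was assessed or, for RCM, every Baseline lesion was assessed or recorded as no longer visible. Otherwise score it as 'Missing', shown as its own category.
2. **Mite totals, burrow totals and regions affected.** Set the subject's value to missing at a visit where a previously affected region was not assessed. This matches the general per-protocol rule in 6.3.1 and needs no imputation.
3. **Reporting.** Tabulate the number of subjects with incomplete region or lesion examinations by dose group and visit.
4. **Sensitivity only.** Carrying counts forward may be added as a sensitivity analysis. It should not be the main rule: 6.10.3.4 carries forward a status and not a count, and bringing a pre-dose count to Day 7 after an active drug could understate the effect.

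The lesion-number category table needs no change.

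The cost is a few lines of text and programming, with no new data. There will be a few more 'Missing' entries and a slightly smaller n for totals, and n may differ between a presence row and its total. Exclusion is not free of bias if missed regions are related to burden, which is why the tabulation in item 3 is needed.
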